10.0 EVALUATION DURING TREATMENT/INTERVENTION

Data collection prior and during hospital admission

Prior to the procedure we will collect:

Baseline parameters: Demographics, tumor characteristics and serum markers that will be routinely collected are: age, sex, comorbidity, body mass index (BMI), tumor size, tumor growth pattern, arterial or venous vascular involvement, nodal status, cancer antigen (CA) 19.9, IgG4, albumin, C-reactive protein (CRP), leukocytes. If IgG4 level is normal at baseline further measurements are not necessary and will therefore not been included in the follow up.

During the hospital stay, we will collect data on serum liver enzymes and inflammatory parameters (WBC, CRP).

Follow up

During follow up, after discharge, patients will be seen in the outpatient clinic, as is routine practice for post-operative/post-procedural patients, for clinical evaluation and laboratory testing of liver enzymes, inflammatory parameters (WBC, CRP), Albumin and tumor markers (CA 19.9).

In this study, patients will also be seen in the outpatient clinic at 2 weeks, 4 weeks, and approximately 6, 12, and 24 months, as is routinely performed for clinical follow-up currently. Laboratory tests obtained at visits after the first post-procedure visit will be determined by the surgeon.

The date of disease progression is defined as the date of CT scan on which the first suspected lesion is defined.

Quality of life will be assessed at the initial clinic visit, initial post-operative visit (2 weeks from surgery), and at subsequent post-operative visits \pm 1 month from 3, 6, 9, 12, and 24 months following the IRE procedure. The Functional Assessment of Cancer Therapy-Hepatobiliary instrument (FACT-Hep) will be used. If patients are unable to complete the questionnaires at the designated visits for any reason, they will be offered the option of returning the QOL via mail.

Imaging

CT and rvRI scans used for routine clinical care will be used for this protocol. If patients are receiving chemotherapy, a pre-chemotherapy scan will be obtained 4-6 weeks post procedure, as per standard clinical practice. If no chemotherapy is planned a scan at 4-6 weeks will be clinically appropriate to assess disease progression, treatment response, and stent patency. Scans every 4-6 months will be used in patients on and off chemotherapy to evaluate for disease progression, which is consistent with current practices for routine management of patients with PHC. Tumor response is defined as a loss of enhancement for hypervascular tumors and as a lack of persistent tumor rim enhancement for hypovascular tumors on contrast imaging studies. Persistent disease is defined as residual tumor enhancement on the posttreatment imaging studies, and local recurrence is defined as an enhancing tumor within 1cm of an ablation zone.

In order to diagnose complications such as biliary leakage, intra-abdominal abscesses or bleeding, ultrasound and CT are used. When disease progression is expected, a CT is performed to confirm (or refute) the clinical suspicion. This procedure is consistent with normal clinical standards.

Follow up of subjects withdrawn from treatment

Patients withdrawn from treatment will not have undergone the RE procedure and are therefore considered not to have participated in this study. These subjects will receive normal follow-up outside this study.

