12.0 CRITERIA FOR THERAPEUTIC RESPONSE/OUTCOME ASSESSMENT

The primary endpoint is biliary drainage patency. This will be measured as a marker of therapeutic response. Biliary drainage patency in patients with metal stents is defined as the period between RE treatment and stent occlusion or patient death. Occlusion of the stent is a clinical event. This is defined as recurrent jaundice with cholestasis, cholangitis (fever, increase in serum bilirubin, leukocytosis), stent failure that leads to replacement of a stent, or need to insert a new drain or stent within 4 months. Biliary drainage patency failure in patients that with plastic drains is defined as patients that cannot have plastic drain removed within 1.5 months of the RE.

The patients and caregivers are told about the symptoms of cholangitis and are asked to contact our hospital immediately in case of signs of obstruction. If stent obstruction is suspected, ERC will be performed and stents are changed if necessary.

Tumor response will not be evaluated in this trial by imaging via RECIST criteria as Klatskin tumors are difficult to measure as they are growing along the biliary tract.

Subjective evaluation of the ablation zone to determine the appearance of an RE associated ablation zone in the hilar area will be performed on postoperative scans.

Persistent disease is defined as residual tumor enhancement on the first post-treatment imaging study, and local recurrence is defined as an enhancing tumor within 1 cm of an ablation zone.

As a secondary endpoint we are measuring overall survival. If there is a response to our treatment, we would expect there may be a longer overall survival.

Response on blood biomarker is defined as decrease of blood marker by >20% from the pre-treatment value.

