14.1 BIOSTATISTICS

The primary objective of this study is to assess biliary drainage patency after IRE treatment of hilar cholangiocarcinoma. In patients with plastic percutaneous drains this is defined as ability to remove plastic biliary drains within 15 months of the IRE procedure without need for reinsertion of a drain or stent. For patients with metal stents in place the definition of patent biliary drainage is 4-months without cholangitis post IRE procedure.

We will enroll 20 patients. Mean patency is approximately 1.5 months for plastic stents and 4 months for metal stents. Assuming an exponential distribution time to failure, we extrapolate that the patency rate at 15 months for plastic stents and at 4 months for metal stents will approximately be 37% and we will use this number as our historical control rate. If 10 or more of the 20 patients we plan to enroll display patency (at 1.5 months for plastic and 4 months for metal stents) then we will recommend IRE for further study. This decision rule has 8% Type I error and 12% Type II error for distinguishing between patency rates of 37% and 65%.

The secondary outcomes of interest are:

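### For metal-stent patients, no patency assessment is scheduled at the 4-month endpoint and no general rule covers unknown status, so a missed event raises the success count

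*Combined protocol and SAP*

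**What the plan says.** Section 14.1 recommends IRE for further study if 10 or more of 20 patients "display patency (at 1.5 months for plastic and 4 months for metal stents"). For metal stents, sections 1.0, 2.1 and 14.1 define success as the absence of cholangitis for 4 months. Section 12.0 lists further forms of occlusion: recurrent jaundice with cholestasis, stent replacement, or a new drain or stent within 4 months.

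The assessments that could establish this status are as follows.

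- **Clinic visits (section 10.0, Follow up):** "patients will also be seen in the outpatient clinic at 2 weeks, 4 weeks, and approximately 6, 12, and 24 months".
- **Blood tests (same place):** "Laboratory tests obtained at visits after the first post-procedure visit will be determined by the surgeon".
- **Quality of life (same place):** the initial visit, 2 weeks after surgery, and post-operative visits within plus or minus "1 month from 3, 6, 9, 12, and 24 months following the IRE procedure". For patients unable to complete the form at the visit, "they will be offered the option of returning the QOL via mail".
- **Scans (section 10.0, Imaging):** one at 4 to 6 weeks, whether or not chemotherapy is given, then every 4 to 6 months to look for progression. Stent patency is a named purpose only of the early scan without chemotherapy.
- **Symptoms (section 12.0):** patients and caregivers are "asked to contact our hospital immediately in case of signs of obstruction".

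Section 13.0 counts withdrawal before 120 days as a patency failure when it is due to complications. The plan gives no rule for loss to contact, withdrawal for other reasons, or status that is simply not known at 4 months.

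**The concern.** Metal-stent success is the absence of an event over a fixed period. Such an endpoint is only as good as the effort to find events, and here that effort thins out when most are expected. A patient treated for cholangitis at a local hospital in month 3 need not appear in the trial record. No section asks about care elsewhere or requires outside records.

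Serious adverse event reporting does not fill the gap. Under section 17.3, routine reporting ends 30 days after the intervention; later events are reportable only if unexpected and at least possibly related. Section 6.2 describes recurrent cholangitis as common in these patients, so an episode in month 3 may well not qualify.

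A missed event moves the metal-stent count in one direction only, towards success. The trial has one arm and 20 patients, treatment is unblinded, and a single count decides the recommendation. One or two misclassified patients can change the conclusion.

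**Working it through.** **1. The plan's own error rates.** Inputs from section 14.1: n = 20, null rate 0.37, target rate 0.65, success at 10 or more, stated errors 8% and 12%. Exact binomial:

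- Cut-off 10: P(X ≥ 10 | 0.37) = 0.165; P(X ≤ 9 | 0.65) = 0.053.
- Cut-off 11: P(X ≥ 11 | 0.37) = 0.078; P(X ≤ 10 | 0.65) = 0.122.

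The stated pair fits a cut-off of 11, not the 10 in the text. That is a separate matter; results below are given for both.

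**2. How much of the metal-stent risk falls after week 4.** Section 14.1 assumes exponential failure with a mean of 4 months for metal stents. Week 4 is 28/30.4375 = 0.92 months.

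- Failed by week 4: 1 − exp(−0.92/4) = 0.205.
- Failed between week 4 and month 4: exp(−0.92/4) − exp(−1) = 0.795 − 0.368 = 0.427.
- Failed by month 4: 1 − exp(−1) = 0.632.
- Share after week 4: 0.427/0.632 = 0.675, or about 67%.

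**3. Effect of missed events.** The documents give neither the number of metal-stent patients nor the share of events missed; both are assumptions. If a share m of post-week-4 metal-stent failures is missed and scored as patent, the apparent metal-stent rate at a true rate of 37% is

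p = 0.37 + 0.63 × 0.675 × m.

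This gives 0.4125 for m = 10% and 0.455 for m = 20%. Plastic-drain patients stay at 0.37. With k metal-stent patients, the total is the sum of Binomial(k, p) and Binomial(20 − k, 0.37). The chance of recommending IRE is then:

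| Metal-stent patients (k) | m = 10%: ≥10 / ≥11 | m = 20%: ≥10 / ≥11 |
|---|---|---|
| none missed | 16.5% / 7.8% | 16.5% / 7.8% |
| 5 | 19% / 9% | 22% / 11% |
| 10 | 22% / 11% | 28% / 15% |
| 15 | 25% / 13% | 35% / 20% |
| 20 | 28% / 15% | 43% / 26% |

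With k = 10, the expected number of post-week-4 failures is 10 × 0.63 × 0.675 = 4.25. So m = 10% means fewer than half a patient missed on average, and m = 20% fewer than one.

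**4. Planned follow-up against the endpoint.** Section 1.0 gives 30 days of follow-up for the primary endpoint. Section 14.1 allows 2 months after the last enrolment to obtain it. Neither reaches the 4 months that the metal-stent definition needs.

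**The case against.** A reader might infer that patients have no visit at all between week 4 and month 6. The documents do not support that. The quality-of-life schedule places a post-operative visit at 3 months plus or minus 1 month, and mail is only a fallback. The clinic list says patients will also be seen at those times, so it need not be exhaustive. Chemotherapy is to be proposed to all patients, preferably starting within 6 weeks, and its duration is an outcome, so treated patients will have contacts in this window. The month-6 visit could recover earlier events by history. All of this stands, and it limits how many events would be missed. It does not close the gap. None of these contacts is stated to establish patency or to ask about care elsewhere. Chemotherapy is optional, and section 9.0 says ongoing cholangitis can rule it out, so patients at higher risk of the event may have fewer contacts.

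A reader might also extend the point to the 1.5-month plastic-drain endpoint. That fails. Clinicians evaluate the drain from day 7, and under section 12.0 a drain that cannot be removed by 1.5 months is a failure. The week-4 visit is close to that date, as is the 4-to-6-week scan: "a pre-chemotherapy scan will be obtained 4-6 weeks post procedure, as per standard clinical practice", and without chemotherapy, "If no chemotherapy is planned a scan at 4-6 weeks will be clinically appropriate to assess disease progression, treatment response, and stent patency". Only a reinsertion elsewhere after removal could be missed.

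Thirdly, it is tempting to say the plan scores every unreported failure as a success. No rule says so. For metal stents it follows from the definition when an event never reaches the record; for patients of unknown status the plan is silent.

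Finally, counting unconfirmed patients as not patent brings a bias of its own, against IRE. That is fair, and its cost is shown under the fix.

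**Conclusion.** The point holds for the metal-stent component. No patency assessment is scheduled at 4 months, detection between planned contacts depends mainly on the patient calling, and no rule covers unknown status beyond withdrawal due to complications before 120 days. A missed event can only raise the success count.

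The size is moderate and rests on assumptions. With 10 metal-stent patients and 10% of their post-week-4 failures missed, the false-positive chance rises from 16.5% to about 22% (7.8% to about 11% at a cut-off of 11). With 20% missed it is about 28% (15%). The exponential model with a 4-month mean is the protocol's own.

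Applying a 10% miss rate to all failures in all 20 patients would give 35.0%. That figure should not be used: it includes plastic-drain patients, whose endpoint defaults to failure, and metal-stent failures before week 4, when visits are scheduled. The excess of 16.5% over the stated 8% comes from the cut-off, not from visit timing.

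The plan should be changed, because the remedy is cheap and lost events may not be recoverable later.

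**What to change.** - **Section 10.0:** add one structured contact at 4 months (plus or minus 2 weeks) for metal-stent patients, by telephone through the research coordinator already assigned. Ask about fever, jaundice, antibiotics, admissions and biliary procedures at any hospital since IRE, and obtain outside records for any positive answer. For plastic-drain patients, ask at an existing contact about drain or stent reinsertion elsewhere.
- **Section 14.1:** score a metal-stent patient as patent only if this contact, or a later visit covering the full 4 months, confirms no event. Otherwise count the patient as not patent. Add a sensitivity analysis that excludes patients of unknown status. Make section 13.0 consistent with this rule.
- **Visit lists:** reconcile the clinic list with the 3- and 9-month quality-of-life visits.
- **Timelines:** extend the primary-endpoint follow-up in sections 1.0 and 14.1 to cover 4 months plus the contact window.

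No extra blood test is needed: section 12.0 treats occlusion as a clinical event, and values near month 4 could be normal after an episode treated in month 3.

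The cost is one call per metal-stent patient, plus record requests where an answer is positive. Patients who cannot be reached count against IRE. If 5% of truly patent metal-stent patients remained unconfirmed (assumption, 10 of 20 with metal stents), their rate at the 65% target becomes 0.65 × 0.95 = 0.6175. Power then falls from 94.7% to 92.8% at a cut-off of 10, or from 87.8% to 84.4% at 11.

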11.1 TOXICITIES/SIDE EFFECTS

In the postoperative period we will observe for known RE-specific toxicities. These include (expected frequency in parentheses):

- Hemorrhage, requiring blood transfusion, radiological, or surgical intervention (3%)
- Hepatic abscess requiring surgery, drainage, or antibiotic therapy alone (5%)
- Biliary stenosis requiring stent placement, bile leakage requiring radiological or surgical intervention (4%)
- Portal hypertension, portobilious fistula, hemobilia, thrombosis of hepatic artery or portal vein (3%)
- Hepatic infarction (3%)
- Large biboma (above 5cm) (3%)
- Liver failure (1%)
- Cardiac arrest, heart attack, cardiac arrhythmia during RE (1%)
- Diaphragmatic paresis (lesion in liver segment VII) (1%)

Expected adverse events associated with the delivery of strong electric pulses are cardiac arrhythmias and severe muscle contractions. To prevent these events, pulses are generally delivered in the refractory period of the heart and with deep muscle paralysis [43]. Despite electrocardiographic synchronization, passage of high-voltage pulses into the body can still cause conduction disturbances in the heart. In a recent published meta-analysis by Scheffer et al., cardiac arrhythmias occurred in 4 of 194 patients (2%), but they were all atrial arrhythmias that resolved spontaneously or within 24 hours after therapy[27]. With the administration of muscle relaxants, no uncontrolled muscle contractions were reported[30, 32, 44-48]. Only Thomson et al. reported a transient increase in systolic blood pressure in all patients directly after RE (20-30 mm Hg), which normalized spontaneously[46].

Retrospective comparison showed that numerous liver capsule punctures during RE did not cause subcapsular hemorrhage and pain after hepatic RE and RF ablation showed similar moderate pain intensity with comparable amounts of self-administered pain medication[49].

12.0 CRITERIA FOR THERAPEUTIC RESPONSE/OUTCOME ASSESSMENT

The primary endpoint is biliary drainage patency. This will be measured as a marker of therapeutic response. Biliary drainage patency in patients with metal stents is defined as the period between RE treatment and stent occlusion or patient death. Occlusion of the stent is a clinical event. This is defined as recurrent jaundice with cholestasis, cholangitis (fever, increase in serum bilirubin, leukocytosis), stent failure that leads to replacement of a stent, or need to insert a new drain or stent within 4 months. Biliary drainage patency failure in patients that with plastic drains is defined as patients that cannot have plastic drain removed within 1.5 months of the RE.

The patients and caregivers are told about the symptoms of cholangitis and are asked to contact our hospital immediately in case of signs of obstruction. If stent obstruction is suspected, ERC will be performed and stents are changed if necessary.

Tumor response will not be evaluated in this trial by imaging via RECIST criteria as Klatskin tumors are difficult to measure as they are growing along the biliary tract.

Subjective evaluation of the ablation zone to determine the appearance of an RE associated ablation zone in the hilar area will be performed on postoperative scans.

Persistent disease is defined as residual tumor enhancement on the first post-treatment imaging study, and local recurrence is defined as an enhancing tumor within 1 cm of an ablation zone.

As a secondary endpoint we are measuring overall survival. If there is a response to our treatment, we would expect there may be a longer overall survival.

Response on blood biomarker is defined as decrease of blood marker by >20% from the pre-treatment value.

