The primary outcome is patency of biliary drainage. In patients with plastic percutaneous drains this is defined as ability to remove plastic biliary drains within 1.5 months of the IRE procedure without need for reinsertion of a drain or stent. For patients with metal stents in place the definition of patent biliary drainage is 4-months without cholangitis post IRE procedure.

Secondary outcomes are the success rate of completing IRE (defined as percentage of planned pulses completed}, complications, duration of hospital stay, quality of life, impact of IRE on post-procedural CT imaging and blood biomarker response, time between IRE and start of palliative chemotherapy, metal stent patency, progression-free and overall survival. Prolonged hospital stay is defined as hospital stay for more than 10 days. The average length of stay for major liver procedures is 8 days. Patients with hilar cholangiocarcinomas often have biliary drains and stents so require extra care as inpatients after any procedure. Complications will be defined as patients experiencing a clinically relevant IRE-related complication within 30 days post-IRE, defined as CTCAE (version 5.0} grade

3 or higher complications requiring re-intervention, prolonged hospital stay, intensive care admission, re-admission or leading to mortality.

Follow up: 30 days after intervention for the primary endpoint. For survival endpoints, there is a 2-year followup.

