beyond the hepatoduodenal ligament have significant longer survival (14 to 16 months) compared to patients with organ metastases (3 to 5 months) [20]. 12% of these patients even survive for more than 36 months [20]. This particular subgroup of PHC patients with primary locally advanced disease may therefore benefit from ablative therapies that counteract tumor growth and potentially improve biliary stent patency and survival. In the past decade, several different ablative techniques like stereotactic body radiation therapy, photodynamic therapy (PDT), (intraductal) radiofrequency ablation (RFA), brachytherapy and microwave ablation have been investigated. Local tumor reduction by PDT in combination with stent therapy is effective for reducing cholestasis. For patients with unresectable hilar cholangiocarcinoma, two randomized studies and several controlled studies have shown an advantage in survival over stenting alone, given improved stent patency [21]. Furthermore, some trials demonstrated a gain in QoL or in performance status [4-7]. But PDT has major limitations such as skin phototoxicity for 3-4 weeks due to the use of slowly degradable photosensitizers in PDT [22]. In addition, thermal ablative modalities (i.e. RFA) are limited by the disadvantages of surrounding tissue heating causing strictures to bile ducts and thromboses to portal vein and

hepatic artery branches and the heat-sink effect. This effect is caused by blood flow in surrounding vessels creating an area where optimal temperatures are not reached, leaving viable cancer tissue *in situ* [23]. This is particularly challenging in PHC because of the typical location in the liver hilum near the portal vein and hepatic artery. Considering these limitations, there is a need to investigate new non-thermal ablative techniques in the treatment of locally advanced PHC.

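### Section 12.0 ends metal-stent patency at death, the other definitions of the primary endpoint are silent on death, and the stated error rates fit neither the printed cut-off nor an endpoint with deaths as failures added to the planning rates

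*Combined protocol and SAP*

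**What the plan says.** Section 12.0 gives the metal-stent endpoint as a duration: "Biliary drainage patency in patients with metal stents is defined as the period between RE treatment and stent occlusion or patient death". Sections 1.0, 2.1 and 14.1 give it as a yes/no outcome, four months after the procedure without cholangitis, and say nothing about death. Section 13.0 counts withdrawal for complications before 120 days as a patency failure but does not cover death. Section 14.1 deals with 30-day deaths only as a safety matter.

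The design is in section 14.1: "We will enroll 20 patients". The control rate rests on this statement: "Mean patency is approximately 1.5 months for plastic stents and 4 months for metal stents". It is converted to 37% under a stated model: "Assuming an exponential distribution time to failure". The decision rule begins "If 10 or more of the 20 patients we plan to enroll display patency", and IRE is then recommended for further study. The claimed properties are: "This decision rule has 8% Type I error and 12% Type II error for distinguishing between patency rates of 37% and 65" per cent. No derivation is given for the 65%.

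Section 3.0 supplies the survival background. Patients with locally advanced or nodal disease "have significant longer survival (14 to 16 months) compared to patients with organ metastases". The same section gives a 12-month overall survival with chemotherapy in patients who are not candidates for resection or transplantation.

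**The concern.** A patient who dies at two months with an open stent has no defined score in the primary count. Section 12.0 points towards failure, although a period that ends at death could also be read as censored there. The wording in section 14.1 could be read as satisfied by a patient who dies without cholangitis. With 20 patients and one count deciding the recommendation, a few such patients can settle the result, so the scoring has to be fixed in advance.

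The error rates are tied to 37% and 65%. If those rates describe stents in surviving patients and deaths are then added as failures, both achievable success rates fall, and power and type I error fall with them. The reader also cannot tell which cut-off the stated errors describe.

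**Working it through.** **1. The plan's own figures, no deaths.** A mean patency equal to the assessment time gives exp(-1) = 0.368, the plan's 37%. (Section 14.1 shows 15 months for plastic drains in two places. I read this as 1.5, as in sections 1.0, 2.1 and 12.0.) With X ~ Binomial(20, p), type I error is P(X ≥ r | p = 0.37) and type II error is P(X < r | p = 0.65):

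| Cut-off r | Type I | Type II |
|---|---|---|
| 10 (as printed) | 16.5% | 5.3% |
| 11 | 7.75% | 12.2% |
| Stated | 8% | 12% |

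The stated pair matches 11 or more, not the printed 10 or more. This discrepancy has nothing to do with death.

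**2. Deaths before 4 months.** The documents give no such figure. I assume exponential survival and read the section 3.0 figures (12, and 14 to 16 months) as medians m. Then S(4) = 0.5^(4/m) is 0.794, 0.820 and 0.841 for m = 12, 14 and 16. The proportion dead is 1 - S(4) = 20.6%, 18.0% and 15.9%, or 4.1, 3.6 and 3.2 of 20 patients.

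**3. Deaths as failures on top of the planning rates.** Further assumptions: deaths are independent of stent failure, and all 20 patients have metal stents. The success rates become 0.65 × S(4) and 0.37 × S(4).

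| m (months) | 0.65 × S(4) | Power, r = 10 | Power, r = 11 | 0.37 × S(4) | Type I, r = 10 | Type I, r = 11 |
|---|---|---|---|---|---|---|
| 12 | 0.516 | 64.3% | 46.9% | 0.294 | 4.2% | 1.45% |
| 14 | 0.533 | 70.0% | 53.1% | 0.304 | 5.2% | 1.88% |
| 16 | 0.547 | 74.1% | 57.9% | 0.311 | 6.0% | 2.26% |

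Without deaths, power is 94.7% at r = 10 and 87.8% at r = 11.

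**4. Dependence on the death rate d and the share of metal stents.** Type II error, with deaths counted only in metal-stent patients:

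| d | All metal, r = 10 | All metal, r = 11 | 10 of 20 metal, r = 10 | 10 of 20 metal, r = 11 |
|---|---|---|---|---|
| 5% | 9.6% | 19.6% | 7.2% | 15.6% |
| 10% | 15.9% | 29.0% | 9.6% | 19.6% |
| 16% | 26.1% | 42.3% | 13.0% | 24.9% |
| 18% | 30.1% | 47.0% | 14.3% | 26.9% |

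At r = 10 with all patients on metal stents, type II error passes 12% only when d reaches about 7.1%. At r = 11 it starts at 12.2%, so any deaths raise it further above the stated figure.

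**5. If 37% and 65% already count deaths as failures,** the success rates do not change and the errors are those in step 1.

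**The case against.** The tempting stronger reading is that both planning rates come from stent failure alone, and that the 12% type II error fails because of deaths. The documents do not support either half. Section 14.1 refers only to mean patency and time to failure. Neither it nor Table 1 in section 3.0 says whether the historical figures counted or censored deaths. The 65% is a target with no derivation, and if it is meant as success on the section 12.0 endpoint, deaths are already inside it. The 12% is also wrong for the printed rule before any death occurs, and at that cut-off a few deaths leave type II error below 12%. These objections stand.

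The size of the effect can also be challenged:

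- The 12-month figure is not specific to this population, since the trial excludes organ metastases. The 14 to 16 months is not labelled a median.
- Section 3.0 reports 12% surviving beyond 36 months, whereas an exponential with median 14 to 16 months gives 0.5^(36/m) = 17 to 21%. A Weibull through both figures (a further assumption) gives about 10 to 15% dead by 4 months. With all patients on metal stents, type II error at d = 10% and 15% is then 15.9 and 24.2% (r = 10) or 29.0 and 40.0% (r = 11).
- Some early deaths would follow a drainage failure that has already been counted, so independence overstates the loss. Even under independence, the expected number of successes lost is 20 × 0.65 × d, or 2.1 to 2.7 patients, not the full 3.2 to 4.1 deaths.
- Type I error falls too, so the harm is not one-sided.

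Each of these reduces the effect. None of them supplies the missing scoring rule.

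A reader might also infer the opposite distortion, with deaths free of cholangitis scored as successes and type I error inflated. The silence in section 14.1 permits that reading, but section 12.0 tells against it, so I place no weight on it.

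**Conclusion.** The point holds as an inconsistency in the primary endpoint together with error rates that need restating. Two parts rest on no assumption about mortality. First, death enters the metal-stent definition in section 12.0 and is absent from sections 1.0, 2.1 and 14.1, with no scoring rule in section 13.0. Second, the stated 8% and 12% belong to 11 or more of 20, while the printed 10 or more has 16.5% and 5.3%.

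The loss of power is conditional. It requires that the planning rates exclude death, and its size depends on early mortality, on independence and on the share of metal stents, none of which the documents give. The all-metal, exponential case (power 64 to 74% at 10, 47 to 58% at 11) is at the upper end. With half the patients on metal stents and 16 to 18% deaths among them, type II error is 13 to 14% at 10 and 25 to 27% at 11. It would be wrong to conclude that deaths are the reason the 12% fails, or that power is necessarily as low as the all-metal figures. Correction is worthwhile because the recommendation rests on one count and the protocol's own survival figures make some deaths before 4 months likely.

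**What to change.** 1. State in sections 1.0, 2.1, 12.0 and 14.1 that death before the read-out is a failure in the primary count, consistent with section 12.0.
2. State that 37% and 65% are success rates on that definition, or adjust them and show the assumed death rate.
3. Reconcile the cut-off with the error rates and restate both type I and type II error for the chosen cut-off on that definition.
4. Report one sensitivity count that excludes patients who died with working drainage.

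The cost is wording, one extra table and possibly a less favourable stated power. Treatment, follow-up and sample size need not change.
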